2.5.5 Unscheduled visits

Unscheduled visit measurements of laboratory data, vital signs, and ECG will be included in the by-visit summaries, computation of baseline, worst values, and PCSAs.

2.5.6 Pooling of centers for statistical analyses

Due to small sample size in some countries, the countries will be pooled into regions as defined below for the analyses:

- East Europe: Poland, Russia, Turkey and Ukraine
- Latin America: Argentina and Chile
- Western countries: USA, Canada, Australia and Germany

2.5.7 Statistical technical issues

Not applicable.

3 INTERIM ANALYSIS

No formal interim analysis is planned. Analyses will be performed for safety/efficacy monitoring and internal decision making. The analyses will be conducted by individuals independent of the study and the development program and reviewed by an independent Data Monitoring Committee (DMC). No formal stopping rules or adjustment for multiplicity will be applied. Full details on DMC procedures and data to be reviewed are described in the DMC charter.

4 DATABASE LOCK

A core database lock is planned to occur approximately 4 weeks after the last EOT visit. The final database is planned to be locked 4 weeks after last patient last visit.

5 SOFTWARE DOCUMENTATION

All summaries and statistical analyses will be generated using SAS version 9.4 or higher.

7 LIST OF APPENDICES

- Appendix A: Potentially clinically significant abnormalities (PCSA) criteria
- Appendix B: Exacerbations of Chronic Obstructive Pulmonary Disease Tool (EXACT)
- Appendix C: COPD Assessment Test (CAT)
- Appendix D: Euroqol Questionnaire (EQ-5D-5L)
- Appendix E: St. George's Respiratory Questionnaire (SGRQ)
- Appendix F: SGRQ Scoring Algorithm
- Appendix G: List of opportunistic infections
- Appendix H: Definition of anaphylaxis
- Appendix I: Low, medium and high dose of inhaled corticosteroids
- Appendix J: Handling of missing data

Appendix A Potentially clinically significant abnormalities criteria

CRITERIA for POTENTIALLY CLINICALLY SIGNIFICANT ABNORMALITIES for phase 2/3 studies (oncology excepted)

(From *BTD-009536 "Analysis and reporting of safety data from clinical trials through the Clinical Study Report" Version 3, 21-MAY-2014*)

Parameter	PCSA	Comments
Clinical Chemistry		
ALT	By distribution analysis : >3 ULN >5 ULN >10 ULN >20 ULN	Enzymes activities must be expressed in ULN, not in IU/L. Concept paper on DILI – FDA draft Guidance Oct 2007. Internal DILI WG Oct 2008. Categories are cumulative. First row is mandatory. Rows following one mentioning zero can be deleted.
AST	By distribution analysis : >3 ULN >5 ULN >10 ULN >20 ULN	Enzymes activities must be expressed in ULN, not in IU/L. Concept paper on DILI – FDA draft Guidance Oct 2007. Internal DILI WG Oct 2008. Categories are cumulative. First row is mandatory. Rows following one mentioning zero can be deleted.
Alkaline Phosphatase	>1.5 ULN	Enzymes activities must be expressed in ULN, not in IU/L. Concept paper on DILI – FDA draft Guidance Oct 2007. Internal DILI WG Oct 2008.
Total Bilirubin	>1.5 ULN >2 ULN	Must be expressed in ULN, not in $\mu\text{mol/L}$ or mg/L . Categories are cumulative. Concept paper on DILI – FDA draft Guidance Oct 2007. Internal DILI WG Oct 2008.
Conjugated Bilirubin	>35% Total Bilirubin and TBILI>1.5 ULN	Conjugated bilirubin dosed on a case-by-case basis.
ALT and Total Bilirubin	ALT>3 ULN and TBILI>2 ULN	Concept paper on DILI – FDA draft Guidance Oct 2007. Internal DILI WG Oct 2008. To be counted within a same treatment phase, whatever the interval between measurement.

CRITERIA for POTENTIALLY CLINICALLY SIGNIFICANT ABNORMALITIES

for phase 2/3 studies (oncology excepted)

(From BTD-009536 "Analysis and reporting of safety data from clinical trials through the Clinical Study Report" Version 3, 21-MAY-2014)

Parameter	PCSA	Comments
CPK	>3 ULN >10 ULN	FDA Feb 2005. Am J Cardiol April 2006. Categories are cumulative. First row is mandatory. Rows following one mentioning zero can be deleted.
CLcr (mL/min) (Estimated creatinine clearance based on the Cockcroft-Gault equation)	<15 (end stage renal disease) ≥15 - <30 (severe decrease in GFR) ≥30 - < 60 (moderate decrease in GFR) ≥60 - <90 (mild decrease in GFR) ≥ 90 (normal GFR)	FDA draft Guidance 2010 Pharmacokinetics in patients with impaired renal function-study design, data analysis, and impact on dosing and labeling
eGFR (mL/min/1.73m2) (Estimate of GFR based on an MDRD equation)	<15 (end stage renal disease) ≥15 - <30 (severe decrease in GFR) ≥30 - < 60 (moderate decrease in GFR) ≥60 - <90 (mild decrease in GFR) ≥ 90 (normal GFR)	FDA draft Guidance 2010 Pharmacokinetics in patients with impaired renal function-study design, data analysis, and impact on dosing and labeling
Creatinine	≥150 µmol/L (Adults) ≥30% change from baseline ≥100% change from baseline	Benichou C., 1994.
Uric Acid Hyperuricemia Hypouricemia	>408 µmol/L <120 µmol/L	Harrison- Principles of internal Medicine 17 th Ed., 2008.
Blood Urea Nitrogen	≥17 mmol/L	
Chloride	<80 mmol/L >115 mmol/L	
Sodium	≤129 mmol/L ≥160 mmol/L	
Potassium	<3 mmol/L ≥5.5 mmol/L	FDA Feb 2005.
Total Cholesterol	≥7.74 mmol/L	Threshold for therapeutic intervention.
Triglycerides	≥4.6 mmol/L	Threshold for therapeutic intervention.
Lipasemia	≥3 ULN	
Amylasemia	≥3 ULN	

CRITERIA for POTENTIALLY CLINICALLY SIGNIFICANT ABNORMALITIES

for phase 2/3 studies (oncology excepted)

(From BTD-009536 "Analysis and reporting of safety data from clinical trials through the Clinical Study Report" Version 3, 21-MAY-2014)

Parameter	PCSA	Comments
Glucose		
Hypoglycaemia	≤3.9 mmol/L and <LLN	ADA May 2005.
Hyperglycaemia	≥11.1 mmol/L (unfasted); ≥7 mmol/L (fasted)	ADA Jan 2008.
HbA1c	>8%	
Albumin	≤25 g/L	
CRP	>2 ULN or >10 mg/L (if ULN not provided)	FDA Sept 2005.
Hematology		
WBC	<3.0 Giga/L (Non-Black); <2.0 Giga/L (Black) ≥16.0 Giga/L	Increase in WBC: not relevant. To be interpreted only if no differential count available.
Lymphocytes	>4.0 Giga/L	
Neutrophils	<1.5 Giga/L (Non-Black); <1.0 Giga/L (Black)	International Consensus meeting on drug-induced blood cytopenias, 1991. FDA criteria.
Monocytes	>0.7 Giga/L	
Basophils	>0.1 Giga/L	
Eosinophils	>0.5 Giga/L or >ULN (if ULN ≥0.5 Giga/L)	Harrison- Principles of internal Medicine 17 th Ed., 2008.
Hemoglobin	≤115 g/L (Male); ≤95 g/L (Female) ≥185 g/L (Male); ≥165 g/L (Female) Decrease from Baseline ≥20 g/L	Criteria based upon decrease from baseline are more relevant than based on absolute value. Other categories for decrease from baseline can be used (≥30 g/L, ≥40 g/L, ≥50 g/L).
Hematocrit	≤0.37 v/v (Male) ; ≤0.32 v/v (Female) ≥0.55 v/v (Male) ; ≥0.5 v/v (Female)	
RBC	≥6 Tera/L	Unless specifically required for particular drug development, the analysis is redundant with that of Hb. Otherwise, consider FDA criteria.
Platelets	<100 Giga/L ≥700 Giga/L	International Consensus meeting on drug-induced blood cytopenias, 1991.

CRITERIA for POTENTIALLY CLINICALLY SIGNIFICANT ABNORMALITIES
for phase 2/3 studies (oncology excepted)
(From BTD-009536 "Analysis and reporting of safety data from clinical trials through the Clinical Study Report" Version 3, 21-MAY-2014)

Parameter	PCSA	Comments
Urinalysis		
pH	≤4.6 ≥8	
Vital signs		
HR	≤50 bpm and decrease from baseline ≥20 bpm ≥120 bpm and increase from baseline ≥20 bpm	To be applied for all positions (including missing) except STANDING.
SBP	≤95 mmHg and decrease from baseline ≥20mmHg ≥160 mmHg and increase from baseline ≥20 mmHg	To be applied for all positions (including missing) except STANDING.
DBP	≤45 mmHg and decrease from baseline ≥10 mmHg ≥110 mmHg and increase from baseline ≥10 mmHg	To be applied for all positions (including missing) except STANDING.
Orthostatic Hypotension		
Orthostatic SDB	≤-20 mmHg	
Orthostatic DBP	≤-10 mmHg	
Weight	≥5% increase from baseline ≥5% decrease from baseline	FDA Feb 2007.

**CRITERIA for POTENTIALLY CLINICALLY SIGNIFICANT ABNORMALITIES
for phase 2/3 studies (oncology excepted)**

(From BTD-009536 "Analysis and reporting of safety data from clinical trials through the Clinical Study Report" Version 3, 21-MAY-2014)

Parameter	PCSA	Comments
ECG		Ref.: ICH E14 guidance (2005) and E14 Q&A (2012), and Cardiac Safety Research Consortium White Paper on PR and QRS (Nada et al. Am Heart J. 2013; 165(4) : 489-500)
HR	<50 bpm <50 bpm and decrease from baseline \geq 20 bpm <40 bpm <40 bpm and decrease from baseline \geq 20 bpm <30 bpm <30 bpm and decrease from baseline \geq 20 bpm >90 bpm >90 bpm and increase from baseline \geq 20bpm >100 bpm >100 bpm and increase from baseline \geq 20bpm >120 bpm >120 bpm and increase from baseline \geq 20 bpm	Categories are cumulative Categories are cumulative
PR	>200 ms >200 ms and increase from baseline \geq 25% > 220 ms >220 ms and increase from baseline \geq 25% > 240 ms > 240 ms and increase from baseline \geq 25%	Categories are cumulative
QRS	>110 ms >110 msec and increase from baseline \geq 25% >120 ms >120 ms and increase from baseline \geq 25%	Categories are cumulative
QT	>500 ms	

[figure not shown]
CRITERIA for POTENTIALLY CLINICALLY SIGNIFICANT ABNORMALITIES

[figure not shown]
for phase 2/3 studies (oncology excepted)

[figure not shown]
(From BTD-009536 "Analysis and reporting of safety data from clinical trials through the Clinical Study Report" Version 3, 21-MAY-2014)

Parameter	PCSA	Comments
QTc	Absolute values (ms)	To be applied to any kind of QT correction formula. Absolute values categories are cumulative
	>450 ms	
	>480 ms	QTc >480 ms and Δ QTc >60 ms are the 2 PCSA categories to be identified in individual subjects/patients listings.
	>500 ms	
	Increase from baseline	
	Increase from baseline]30-60] ms	
	Increase from baseline >60 ms	

[figure not shown]

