2.1.4.3 Laboratory safety variables

Clinical laboratory data consists of blood analysis, including hematology, clinical chemistry, and urinalysis. Clinical laboratory values after conversion will be analyzed in standard international units and international units will be used in all listings and tables.

Blood samples for clinical laboratories will be taken at Visits 1, 2, 6, 10, 14, 20, EOT, EOS and early termination unless otherwise specified. The laboratory parameters will be classified as follows:

- Hematology
 - **Red blood cells and platelets and coagulation:** hemoglobin, hematocrit, total red blood cell count, platelet count
 - **White blood cells:** total white blood cell (WBC) count, neutrophils, lymphocytes, monocytes, basophils, eosinophils
- Clinical chemistry
 - **Metabolism:** glucose, total cholesterol, total protein, creatine phosphokinase, albumin
 - **Electrolytes:** sodium, potassium, chloride, bicarbonate
 - **Renal function:** creatinine, estimated creatinine clearance (Cockcroft's formula in [Section 2.5.1](#)), blood urea nitrogen, uric acid
 - **Liver function:** alanine aminotransferase, aspartate aminotransferase, alkaline phosphatase, lactate dehydrogenase, total bilirubin (in case of values above the normal range, differentiation in conjugated and non-conjugated bilirubin)
 - **Pregnancy test:** serum beta-human chorionic gonadotropin (β -hCG) will be performed at Visit 1 in women of childbearing potential
 - **Hepatitis screen:** clinical laboratory testing at Visit 1 will include hepatitis screen covering hepatitis B surface antigen (HBs Ag), hepatitis B surface antibody (HBs Ab), hepatitis B core antibody (HBc Ab), and hepatitis C virus antibody (HCV Ab).
 - **QuantiFERON-TB Gold / Plus** will be tested at Visit 1
 - **Human immunodeficiency virus (HIV) screen:** anti-HIV-1 and HIV-2 antibodies will be tested at Visit 1

- **Anti-nuclear antibody (ANA)** will be tested at Visit 1

Note: Anti-ds DNA antibody will be tested if ANA is positive ($\geq 1:160$ titer).

Urine samples will be collected:

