2.4.5 Analyses of safety data

The summary of safety results will be presented by treatment group.

General common rules

All safety analyses will be performed on the safety population as defined in [Section 2.3.2](#), unless otherwise specified, using the following common rules:

- Safety data in patients who do not belong to the safety population will be listed separately.
- The baseline value is defined as the last available value prior to the first dose of the IMP.
- The potentially clinically significant abnormality (PCSA) values are defined as abnormal values considered medically important by the Sponsor according to predefined criteria/thresholds based on literature review and defined by the Sponsor for clinical laboratory tests, vital signs, and ECG (PCSA version dated May 2014, see [Appendix A](#)).
- PCSA criteria will determine which patients had at least 1 PCSA during the treatment-emergent adverse event period, taking into account all evaluations performed during the treatment-emergent adverse event period, including nonscheduled or repeated evaluations. The number of all such patients will be the numerator for the on-treatment PCSA percentage.
- The treatment-emergent PCSA denominator by group for a given parameter will be based on the number of patients assessed for that given parameter in the TEAE period by treatment group on the safety population.
- For quantitative safety parameters based on central laboratory/reading measurements, descriptive statistics will be used to summarize results and change from baseline values by visit and treatment group. Summaries will include the endpoint value. The endpoint value

is commonly defined as the value collected at or just prior to the last dose date +14 days, or at the end of treatment visit, whichever comes later. If this value is missing, this endpoint value will be the closest value prior to the last dose intake. The worst value is defined as the nadir and/or the peak post-baseline (up to last administration of IMP) according to the direction (minimum or maximum) of the abnormality as defined in the PCSA list.

- The analysis of the safety variables will be essentially descriptive and no systematic testing is planned.

All safety values including unscheduled measurements will be assigned to the appropriate safety analysis visit window defined in [Section 2.5.4](#).

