2.4.5.3 Analyses of laboratory variables

The summary statistics (including number, mean, median, Q1, Q3, standard deviation, minimum and maximum) of all laboratory variables (central laboratory values and changes from baseline) will be calculated for each visit or study assessment (baseline, each post-baseline time point and last on-treatment) by treatment group. For each continuous parameter listed in [Section 2.1.4.3](#), mean changes from baseline with the corresponding standard error will be plotted over time in each treatment group. This section will be organized by biological function as specified in [Section 2.1.4.3](#).

The incidence of PCSAs (list provided in [Appendix A](#)) at any time during the TEAE period will be summarized by biological function and treatment group whatever the baseline level and/or according to the following baseline status categories:

- Normal/missing
- Abnormal according to PCSA criterion or criteria

For parameters for which no PCSA criteria are defined, similar table(s) using the normal range will be provided.

Laboratory measurements obtained at either scheduled or unscheduled visits will be used in analyses of PCSA. In addition, both centralized and local test results will be used. Centralized data will be used preferentially to the local measures in the analysis when several measurements are performed on the same date and at the same time for a given laboratory test.

Listings will be provided with flags indicating the out of range values as well as the PCSA values.

Potential drug-induced liver injury

The liver function tests, namely AST, ALT, alkaline phosphatase and total bilirubin will be used to assess possible drug-induced liver toxicity. The proportion of patients with PCSA values at any post-baseline visit will also be displayed by duration of exposure for each treatment group.

A graph of distribution of peak values of ALT versus peak values of total bilirubin will also be presented on a logarithmic scale. The graph will be divided into 4 quadrants with a vertical line corresponding to 3 x ULN for ALT and a horizontal line corresponding to 2 x ULN for total bilirubin.

Listing of selected laboratory parameters for possible Hy's law cases identified by treatment group (eg, patients with any elevated ALT >3 x ULN, and associated with an increase in bilirubin ≥ 2 x ULN) will be provided.

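### SAP Appendix A lists normal creatinine clearance (≥90 mL/min) as a potentially clinically significant abnormality, so under the literal rule every assessed patient is a case

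*SAP*

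**What the plan says.** SAP 2.4.5 (general common rules) says that PCSA values are "defined as abnormal values considered medically important by the Sponsor" and sets the counting rule: "PCSA criteria will determine which patients had at least 1 PCSA during the treatment-emergent adverse event period". The denominator is the number of patients assessed for the parameter in that period.

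SAP 2.1.4.3 makes CLcr a planned variable; the renal function list reads "creatinine, estimated creatinine clearance (Cockcroft's formula in" and points to the formula in 2.5.1.

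The PCSA column of SAP Appendix A gives these CLcr bands in mL/min: "<15 (end stage renal disease) ≥15 - <30 (severe decrease in GFR", then "≥30 - < 60 (moderate decrease in GFR", then "≥60 - <90 (mild decrease in GFR) ≥ 90 (normal GFR". The eGFR row repeats them.

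SAP 2.4.5.3 plans PCSA incidence by arm regardless of baseline and/or by baseline status. Baseline status has two groups: normal/missing, and "Abnormal according to PCSA criterion or criteria". SAP 2.5.3 puts patients with no baseline value in the first group.

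**The concern.** A class that the appendix itself labels normal stands in a column reserved for abnormal values. No sentence in the SAP exempts it or says that the CLcr bands are only descriptive. The fallback to the normal range in 2.4.5.3 applies only to parameters without PCSA criteria, so it does not help here.

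The baseline split exists to separate patients who become abnormal on study from those who already were. Protocol exclusion E 37 rules out creatinine of 150 µmol/L or more at screening but leaves room for reduced clearance at entry, so the separation has a use for CLcr. As written, the row either cannot make that separation or adds improvement to the PCSA counts. The listings required by 2.4.5.3 would also flag every CLcr record as a PCSA.

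**Working it through.** The plan states no figure to reproduce. The check is whether the bands leave any value uncounted, and what follows under each reading of the rule.

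**1. Coverage of the bands.** Inputs are the five Appendix A bands: <15, 15 to <30, 30 to <60, 60 to <90, and ≥90 mL/min. On a grid from 0 to 300 mL/min in steps of 0.01, with the cut points, values just below them and one extreme value added, every value meets exactly one band (minimum 1, maximum 1). With the ≥90 band removed, values of 90 or more meet none.

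**2. Examples with the SAP 2.5.1 formula.** CLcr = (140 − age) × weight × (1 − 0.15 × sex) / (0.814 × creatinine), with sex 0 for men and 1 for women. The patients are invented.

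| Patient | Calculation | CLcr | Band met |
|---|---|---|---|
| Man, 60 y, 80 kg, 80 µmol/L | 80 × 80 / (0.814 × 80) | 98.3 | ≥90 |
| Woman, 65 y, 70 kg, 70 µmol/L | 75 × 70 × 0.85 / (0.814 × 70) | 78.3 | 60 to <90 |
| Woman, 75 y, 60 kg, 90 µmol/L | 65 × 60 × 0.85 / (0.814 × 90) | 45.2 | 30 to <60 |
| Man, 75 y, 55 kg, 149 µmol/L | 65 × 55 / (0.814 × 149) | 29.5 | 15 to <30 |

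The first patient is normal by the appendix's own label and still meets a listed criterion. The last has a creatinine just inside the E 37 limit, which shows that low clearance at entry is possible.

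**3. Any-PCSA count.** Each assessed patient has at least one value and each value meets a band, so numerator equals denominator: 100% in both arms.

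**4. Baseline split.** It depends on how the bands are read.

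- *Bands pooled.* Every measured baseline meets a criterion and is abnormal. The normal/missing group holds only missing baselines. A patient who falls from 95 to 45 and one who stays at 45 fall in the same baseline group.
- *Bands separate.* A patient at 95 does not meet the 30 to <60 criterion and is baseline-normal for that row, so the split works for the lower rows. The ≥90 row then counts improvement. For a man of 60 weighing 80 kg, CLcr = 6400 / (0.814 × creatinine) = 7862.4 / creatinine. A drop in creatinine from 92.5 to 82.8 µmol/L moves him from 85.0 to 95.0 and into the ≥90 PCSA row.

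**5. What the creatinine row already covers.** Its Appendix A criteria are ≥150 µmol/L and changes from baseline of ≥30% and ≥100%. With weight and age fixed, CLcr is inversely proportional to creatinine, so a 30% rise is a fall in CLcr of 1 − 1/1.3 = 23%. Large falls are therefore caught. A smaller fall across 60 need not be: for the same man, 65 to 55 mL/min is creatinine 7862.4/65 = 121.0 to 7862.4/55 = 143.0, a rise of 18% that stays below 150.

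**6. After the change.** With ≥90 as the reference class, values of 90 or more meet no criterion, incidence can fall below 100%, and patients with a baseline of 90 or more form a measured normal group.

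**The case against.** The strongest reply is that 2.4.5 already excludes a normal value by definition, so the ≥90 line can only be a reference class. The row looks like a renal-function classification carried over from a sponsor template; its comment cites a guidance on impaired renal function, and it lacks the note on cumulative categories given for ALT, AST and CPK. A programmer could reasonably treat ≥90 as the reference. This is probably the intent, but the SAP does not say so, and its counting rule points to the listed criteria. The definition and the list conflict, and the text should settle which governs.

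It can also be said that the two baseline problems need different readings. That is right: pooled bands empty the baseline-normal group, separate bands count improvement, and both cannot occur at once. Each reading still leaves one defect.

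Three further points stand and limit the size. The baseline split is planned as and/or, the safety analysis is descriptive with no systematic testing, and the <15, 15 to <30 and 30 to <60 rows remain informative by arm if shown on separate lines.

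**Conclusion.** The point holds at low severity. The SAP contradicts itself on what a CLcr PCSA is. The 100% figure follows from the printed bands and the counting rule alone and needs no assumption about the patients; it does assume that the rule is applied literally. How many patients would enter the ≥90 row depends on age, weight and creatinine distributions that the documents do not give.

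A reader might infer more than the documents support:

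- *That renal safety cannot be assessed, or rests on this table.* It does not. Appendix A has working criteria for creatinine and blood urea nitrogen (≥17 mmol/L), and 2.4.5.3 provides by-visit summaries and mean-change plots that include CLcr.
- *That the eGFR row doubles the problem.* SAP 2.1.4.3 does not list eGFR, so that row matters only if eGFR is reported.
- *That a normal baseline should mean 60 or more.* The appendix labels 60 to <90 a mild decrease, so this would exchange one inconsistency for another.

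No hypothesis test, primary endpoint or decision rule is affected.

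**What to change.** 1. In SAP Appendix A, state that ≥90 mL/min is the normal reference class for CLcr and not a PCSA, and that a normal CLcr baseline means ≥90. Apply the same note to the eGFR row if eGFR will be reported.
2. In SAP 2.4.5.3, add a CLcr shift table by arm, from baseline band to lowest band in the TEAE period. Protocol Table 15 promises shift tables for laboratory parameters, SAP 2.4.5.3 specifies none, and SAP 1.5 does not list their removal. The table lets new falls below 60, 30 or 15 be read directly. The first change alone would not do this, because a patient who falls from 85 to 45 would still be in the abnormal baseline group.

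The cost is a short Appendix A note and one table from data already collected. The only drawback is a small departure from the sponsor's template row.
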